6.0 STATISTICAL CONSIDERATIONS

6.1 Study Design

MDS-TAO is a prospective, observational study comparing OS between patients aged 60-75 who undergo RIC HSCT for MDS (Group A) and patients 60-75 who do not undergo HSCT but who have disease of sufficiently high enough risk to warrant HSCT and who are also fit enough to undergo the procedure (Group B).

6.2 Sample Size

290 eligible patients will be enrolled between the two groups over a period of 5 years and followed for an additional 5 years. Based on our current practice, we anticipate that the enrollment will be 1:2 ratio for Group A (HSCT) to Group B (no HSCT). This design will give approximately 85% power to detect a 15% difference in 5-year OS between the two study groups.

6.3 Accrual

[figure not shown]
In 2009, the DFCI performed 18 RIC HSCTs in patients similar to the ones who will be eligible for the MDS-TAO study. Given the addition of the other members of the DF/HCC (BIDMC and MGH), we anticipate that we will accrue 20 patients per year for the HSCT group (Group A). There were also 50 patients seen at DFCI in 2009 with MDS of sufficiently high risk by WHO category (RAEB-1, RAEB-2, RCMD, and RCMD-RS) to be considered for HSCT but who did not ultimately receive HSCT. Thus, we project that we will accrue at least 40 patients per year who will enter MDS-TAO but not go on to HSCT (Group B). With 60 patients per year, we anticipate that accrual will be complete in 5 years.

6.4 Primary Outcome

The primary endpoint of this study is 5-year OS. OS is defined as time from study entry to death from any cause. Alessandro et al³⁹ recently reported the impact of WPSS on the outcome of MDS patients who underwent allogeneic HSCT. According to their report, the 5-year OS after HSCT was 51% in RAEB-1 and 28% in RAEB2 with an indication of plateau after 5-6 years post transplant. This observation resembles our experience at DFCI with RIC HSCT for older patients with MDS. Malcovati et al³⁶ reported that 5-year OS was 3% in the RAEB-1 group and 14% in the RAEB-2 group among 426 MDS patients who did not undergo HSCT. Most of the patients in these studies, however, were treated prior to the wide use of DNA-methyltransferase inhibitors. Thus, extrapolating this information and based on our experience at DFCI, we hypothesize that a small portion of patients will be cured with HSCT from the underlying disease and the 5-year OS will be 25%, whereas the 5-year OS will be 10% for the non-HSCT patients and the survival distribution of these patients will follow an exponential distribution. In addition, we expect that there will be an approximately 4-6 month wait time for patients in Group A from enrollment to actual RIC HSCT, thus no difference in OS between the two groups is expected for some period after the start of the study. Based on this information and assumptions, we propose an alternative hypothesis as: $H_a: S_A > S_B$, where S_A denotes the survival distribution of Group A and S_B denotes the survival distribution of Group B. Specifically:

$$S_A = 0.19 + 0.4 \cdot \exp(-t \cdot (\log(2)/10)) + 0.41 \cdot \exp(-t \cdot (\log(2)/20)); \text{ and } S_B = \exp(-t \cdot (\log(2)/18)).$$

The figure depicts these two survival distributions graphically. With this design, 290 patients

will be required to achieve 85% power with one-sided significance level of 0.025. This power calculation is calculated using the R program *Powgrnk* (developed by [name] at DFCI), which computes power of the two-group log-rank test for arbitrary failure time distributions.

6.5 Interim Analyses

The study will be monitored using standard procedures and processes. Interim inspections will occur annually; however, as this is an observational study and no new treatment is proposed, it is important to note that these interim analyses will not have an effect in terms of stopping accrual to the study or to terminate the study early in favor of alternative or null hypothesis.

6.6 Secondary Outcomes

Secondary outcomes include PFS and changes in self-reported QoL. PFS is defined as time from enrollment until evidence of progression to acute leukemia (time until increase in marrow or peripheral blasts to >20%). QoL will be assessed via changes between baseline and two-year assessments on the EORTC-30 and QUALMS-1. We also plan baseline assessment of IPSS and WPSS, number of cytopenias, transfusion dependence, disease duration at baseline, prior therapies and age at HSCT. Of note, we have not based our power calculations on these outcomes and covariates due to their exploratory nature.

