3.2 Secondary Objectives

1. To prospectively compare the progression-free survival (PFS) of patients in Group A to that of patients in Group B as defined above (**secondary outcome**).
2. To prospectively compare changes in the quality of life (QoL) from baseline to two years of patients in Group A to that of patients in Group B as defined above (**secondary outcome**).

3. To assess the potential association of patient- and disease-specific factors—including International Prognostic Scoring System (IPSS) score, WHO-based Prognostic Scoring System (WPSS) score, number of cytopenias, transfusion dependence, disease duration at baseline, prior therapies and age at HSCT—with the primary and secondary outcomes.

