6.7 Statistical Analysis Plan

As a patient's status in Group A may be changed during the study from waiting for HSCT to being a HSCT recipient, the effect of HSCT will be assessed in a various ways. Our first approach will be using the Mantel-Byer method.⁴⁰ Mantel and Byer (1974) proposed a modified life table to avoid 'time-to-treatment' bias and to accommodate the transient nature of transplant status. The second approach is to treat patient's transplant status as a time-dependent function, $X=X(t)$, as proposed by Crowley and Hu.⁴¹ In this approach, $X(t)$ is an indicator variable at time t , that is, $X(t)=0$ if the patient has not received the transplant at time t , and 1 if the patient has received the transplant at time t . Age at HSCT will be constructed in a similar manner. Another approach is a landmark analysis at one year after study entry.⁴² We will also explore a combination of a pointwise comparison of survival curves at specified time t and a log-rank test after t , using the method proposed by Logan et al.⁴² The last two approaches are particularly suitable as the overall survival between the two groups is not expected to be different during the first year of study, but instead start to separate after approximately one year.

QoL will be assessed using the EORTC-30³⁷ and the QUALMS-1, a disease-specific measure developed by [name] and colleagues at DFCI which is currently undergoing validation.³⁸ The predictability of IPSS or WPSS score on survival outcome will be assessed using the time-dependent ROC curve estimation for censored survival data (survival ROC), proposed by Heagerty et al.⁴⁴⁻⁴⁵ The predictability of these two scoring systems will be compared in each group. In addition, a subset analysis will be performed for Group A (HSCT) to prospectively determine if disease- or patient-related factors predict outcomes of HSCT for MDS in patients aged 60-75. These factors include baseline age at HSCT, IPSS score, WPSS score, number of cytopenias, transfusion dependence, disease duration, prior therapies, and Sorror co-morbidity index. In this subset analysis, standard time-to-event analysis as well as competing risks data analysis⁴⁶ will be performed.

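### PFS in section 6.6 counts only progression to AML and leaves death unaddressed for Group A versus Group B, so the first secondary objective would report time to AML under a PFS label

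*Combined protocol and SAP*

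**What the plan says.** All references are to the combined protocol and SAP.

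- Section 3.2 makes PFS the first secondary objective: "To prospectively compare the progression-free survival (PFS) of patients in Group A to that of patients in Group B". It gives no definition of its own.
- Section 6.6 holds the only definition: "PFS is defined as time from enrollment until evidence of progression to acute leukemia", explained in parentheses as "time until increase in marrow or peripheral blasts to >20" per cent. Death is not mentioned.
- Section 6.4 does name death, but for the primary endpoint only: "OS is defined as time from study entry to death from any cause".
- Section 6.7 lists the methods for the transplant effect, beginning with "Our first approach will be using the Mantel-Byer method". It then lists a time-dependent covariate, a one-year landmark, and a pointwise comparison combined with a later log-rank test. None says what a death without AML counts as when the outcome is PFS.
- Competing risks appear once in 6.7, in the analysis of prognostic factors within Group A: "In this subset analysis, standard time-to-event analysis as well as competing risks data analysis".
- On the standing of these outcomes, 6.6 says "we have not based our power calculations on these outcomes and covariates due to their exploratory nature".

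**The concern.** Readers take PFS to include death. An analyst who follows 6.6 to the letter will produce time to AML, while one who follows convention will produce AML or death. Both could claim to have followed the plan.

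The gap matters because death without AML is plausible in both groups. Section 2.0 describes severe MDS as accompanied by bleeding, infection and rapid mortality, and it cites transplant-related mortality of 28% and 5% in two reduced-intensity series. If such deaths are censored, a main harm of transplant drops out of PFS, and so do non-leukemic deaths in Group B. Section 8.0 says the results are meant to help payers judge whether the procedure improves outcomes, so a mislabelled secondary endpoint could be misread.

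**Working it through.** **1. The plan's own figures.** With t in months, the curves in 6.4 give:

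- S_A(60) = 0.19 + 0.4·2^(−6) + 0.41·2^(−3) = 0.19 + 0.00625 + 0.05125 = 24.75%
- S_B(60) = 2^(−60/18) = 9.9%

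These match the stated assumption, "the 5-year OS will be 25%, whereas the 5-year OS will be 10% for the non-HSCT patients". A simulated one-sided 0.025 log-rank test with 97 and 193 patients, uniform accrual over 60 months and 60 more months of follow-up has 83.2% power (84.8% with 100 and 200), against about 85% stated. The plan states no figure for PFS.

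**2. How common death is.** S_A(24) = 44.4% and S_B(24) = 39.7%, so 56% and 60% are expected to have died by two years. Over the whole study the mean survival at a uniform 60–120 months of follow-up is 21.3% (A) and 3.9% (B). Expected deaths are 97 × 0.787 + 193 × 0.961 = 76.3 + 185.5, or about 262 of 290.

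**3. Why the label fails.** With death counted, PFS(t) is the probability of being alive and AML-free, so it cannot exceed OS(t). With AML as the only event and death competing, the reported figure is P(alive, AML-free) + P(dead without AML). It exceeds OS by P(dead without AML) − P(alive with AML).

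**4. A closed-form example (assumed hazards).** Let AML occur at 0.015 per month in both groups, and death without AML at 0.03 (A) and 0.01 (B).

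- AML only, deaths censored: 1 − exp(−0.015×24) = 30.2% AML at 24 months in both groups, HR 1.0.
- Death counted: exp(−0.045×24) = 34.0% (A) and exp(−0.025×24) = 54.9% (B), HR 0.045/0.025 = 1.80.

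If the two death hazards are swapped, the HR with death counted is 0.56. If both are 0.02, it is 1.0. The AML-only HR is 1.0 in all three cases.

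**5. Illustration on the plan's curves.** Death times were drawn from S_A and S_B. These assumptions are not in the documents:

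- HSCT takes place at a uniform 4–6 months.
- Transplant-related mortality (TRM) is 0, 5 or 15% of Group A, taken from its deaths in the 12 months after HSCT.
- AML precedes 30, 40 or 50% of all other deaths, with the same share in both groups.
- The lead time from AML to death is exponential with mean 6 months.
- Groups are fixed from enrollment, as in the plan's power calculation.

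| Five-year value | A | B | Gap (points) |
|---|---|---|---|
| OS | 25% | 10% | 15 |
| AML only, deaths without AML censored | 51–72% | 32–52% | 16–25 |
| AML only, deaths without AML competing | 62–82% | 54–73% | about 5–15 |
| AML or death | 24–25% | 9% | 15 |

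Between 131 and 188 of the 262 deaths would not be PFS events. At an AML share of 50%, raising TRM from 0 to 15% lifts Group A's censored AML-only value from 51% to 57%, so more transplant deaths make transplant look better. Even with AML before 90% of deaths and no TRM, the censored values are about 28% and 11%, still above OS. At TRM 5%, changing the mean lead time to 1, 3 or 12 months gives 52–69% (A) and 32–53% (B), so lead time matters little.

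**6. Hazard ratios under the same assumptions, deaths censored.**

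| Method | OS | AML only, TRM 0 / 5 / 15% | AML or death |
|---|---|---|---|
| Log-rank, fixed groups | 0.68 | 0.69–0.70 / 0.65–0.66 / 0.56–0.57 | 0.67–0.68 |
| Mantel-Byar | 0.62 | 0.58–0.59 / 0.55–0.56 / 0.48–0.50 | 0.59–0.62 |

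With unequal AML shares at TRM 5%, the Cox HR for AML only is 0.85 when the share is 40% in A and 30% in B, and 0.46 when reversed. AML or death stays at 0.65–0.67.

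**The case against.** **The wording is open rather than wrong.** The endpoint's name contains the word survival, and 6.6 could be read as defining progression only, with death implied. But the sentence defines PFS itself, and 6.4 shows that death was written in where it was meant to count. Read literally, the rule gives time to AML.

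**The consequence is limited.** This stands. The secondary outcomes are called exploratory, OS captures every death, and power and sample size rest on OS alone. That caps the severity, but it does not justify a label that contradicts its definition.

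**The size rests on outside assumptions.** This also stands. With equal AML shares and no TRM, the log-rank HRs for AML only and for AML or death are practically equal; the shift comes from assumed TRM or unequal shares. TRM above 15% was not tabulated. In Group A, 28% is the most the curves allow within 12 months of HSCT (S_A(5) − S_A(17) = 27.7%), but a 24-month window would allow 42%. The Mantel-Byar figures also let Group A patients die before HSCT (1 − S_A(5) = 18%), although the plan defines Group A by receipt of HSCT. The hazard ratios show sensitivity, not an expected bias.

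**The composite is not full PFS either.** Adding death still leaves out relapse or progression of MDS short of AML. That is fair, and the write-up should say what the endpoint covers. Renaming it as time to AML with death competing would also remove the contradiction, but would leave 3.2 without a PFS comparison.

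**Conclusion.** The definition is wrong as written. Applied literally, 6.6 delivers time to AML for an objective that promises PFS, and the handling of death in the A versus B comparison is unstated. This follows from the text and needs no simulation.

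The size can only be illustrated. Under the assumptions above, the five-year gap ranges from about 5 to 25 points depending on a rule the plan leaves open, against 15 points when death counts. Reported PFS would exceed OS in both groups across the whole range examined. The direction of any bias depends on how deaths split by cause, which the documents do not give. The primary OS analysis and the sample size are untouched. This should be corrected before analysis, because a later change would look data-driven.

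**What to change.** In 6.6, define PFS as the time from enrollment to whichever comes first, progression to AML or death from any cause. Patients alive and free of AML are censored at their last assessment. State that progression short of AML is not an event.

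In 6.7, state that the A versus B comparison of PFS uses the same time-dependent methods as OS. If time to AML is also wanted, report it under that name, with death without AML as a competing event in the A versus B comparison and not only within Group A.

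A minor point to settle in the same edit: 6.6 uses a blast threshold above 20%, while exclusion criterion 1 in 4.2 uses 20% or more. A patient at exactly 20% is excluded at entry but would not be a progression event, so the two should be reconciled.

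The cost is two or three sentences. Deaths are already collected for OS, so no new data are needed.

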4.2 Exclusion Criteria

1. Known baseline conversion to AML (eg, $\geq 20\%$ peripheral or marrow blasts).
2. Knowledge of potential donor status at study entry. Of note, knowledge of HLA status WITHOUT a related or unrelated search is allowed.
3. History of prior malignancy within the past year, except for adequately-treated carcinoma in situ of uterine cervix, basal cell or squamous cell skin cancer.
4. Any severe concurrent disease, infection, or comorbidity that, in the judgment of the principal investigator, would make the patient inappropriate for HSCT at the time of study entry.
5. Psychiatric disorders including dementia that would preclude obtaining informed consent or the ability to participate in an ongoing research study.

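### Section 6.6 counts progression to acute leukemia only above 20% blasts, while exclusion criterion 1 places 20% itself within AML, so a reading of exactly 20% is classified in two ways

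*Combined protocol and SAP*

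**What the plan says.** Two places in the combined protocol and SAP attach a blast percentage to acute leukemia.

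- **At entry (section 4.2, exclusion criterion 1):** "Known baseline conversion to AML (eg, $\geq 20\%$ peripheral or marrow blasts". The inequality includes 20%, and the figure is introduced as an example.
- **On study (section 6.6):** "PFS is defined as time from enrollment until evidence of progression to acute leukemia", followed in parentheses by the working rule "time until increase in marrow or peripheral blasts to >20" percent. The inequality is strict.

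PFS is the first of the secondary objectives. Section 3.2 states the aim as "To prospectively compare the progression-free survival (PFS) of patients in Group A to that of patients in Group B". Section 5.1 says that outcomes for patients who are not transplanted come from Leukemia CRIS, while those for transplanted patients come from the CIBMTR SCTOD. No other section gives a blast threshold for acute leukemia or a rule that reconciles these two.

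**The concern.** Both rules describe the same disease state in the same compartments, marrow and blood, so one would expect a single cut-off. As written, the state that bars a patient from the study at 20% is not yet an event for a patient already in it.

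What is at stake is the classification and dating of PFS events at that one value. Section 6.6 names no PFS event other than progression to acute leukemia, and its blast rule is the only criterion it gives for that event. A reading of exactly 20% is plausible: RAEB-2 is eligible under section 4.1, and entry is barred only from 20% upward, so some patients may enrol not far below the line. Twenty is also a round number for a reported count. Anyone abstracting such a result would find two answers in one protocol. Because the two groups' outcomes come from different databases, the protocol needs to give one answer that both sources can follow.

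**Working it through.** The plan gives no figure to reproduce here, and the point depends on no sample size, power or event count. The check sets the two rules side by side at and around the boundary.

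**Inputs**

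- Entry rule (section 4.2, exclusion criterion 1): AML if blasts ≥ 20%, peripheral or marrow.
- PFS rule (section 6.6): event if blasts > 20%, marrow or peripheral.

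**Boundary check**

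| Blasts | Entry rule (≥ 20%) | PFS rule (> 20%) | Agree? |
|---|---|---|---|
| 19% | 19 ≥ 20 false: not AML | 19 > 20 false: no event | Yes |
| 20% | 20 ≥ 20 true: AML | 20 > 20 false: no event | **No** |
| 21% | 21 ≥ 20 true: AML | 21 > 20 true: event | Yes |

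The rules differ at exactly 20% and nowhere else.

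**What follows for an enrolled patient whose first AML-range reading is 20%**

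- *20%, later 21%.* The literal rule in section 6.6 dates the event at the second sample. A rule of 20% or more dates it at the first. The event is kept but dated late, by the time between the two samples.
- *20%, later 19% and never above 20%.* The literal rule records no event at all. A rule of 20% or more records one at the first sample. The event is lost.

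**What cannot be computed**

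- *How many patients.* The documents give no distribution of blast counts at conversion. Any share would be an assumption, and the true share could be close to zero.
- *How long the delay.* Sections 5.1 and 5.2 set outcome assessments every 6 months for 3 years and yearly after that. These are times for assessing outcomes and updating records, not for taking blood or marrow samples. A result obtained between assessments could date the event sooner.

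**What is untouched**

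The primary endpoint in section 6.4 is OS, counted to death from any cause, and uses no blast count. The 290 patients and 85% power in sections 6.2 and 6.4 rest on OS alone.

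**The case against.** The strongest reply is that the text is softer than two formal definitions. Exclusion criterion 1 offers its figure as an example. In section 6.6 the event is evidence of progression to acute leukemia, and the blast figure is a gloss in parentheses. A patient diagnosed with acute leukemia at 20% could reasonably be recorded as having progressed. On that reading, the late or missing event arises only if the parenthesis is applied as an exhaustive rule. This stands as a limit on how often the mismatch would matter in practice. It does not remove the mismatch: the example still puts 20% inside AML, the gloss still leaves it out, and nothing says that a diagnosis overrides the gloss.

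The second reply is about weight. Of the secondary outcomes the plan says "we have not based our power calculations on these outcomes and covariates due to their exploratory nature". The same definition does not mention death as an event, which is a separate and larger question about this endpoint. Both remarks are fair. They bear on priority, not on whether the wording is consistent.

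A reader might go further and infer that the mismatch biases the comparison of Group A with Group B, for instance because a transplant soon after a 20% reading lowers the blasts and removes the event. The documents do not support that. It would take a first reading of exactly 20%, no recorded diagnosis of leukemia, treatment that lowers the blasts before any sample exceeds 20%, and an imbalance in all this between the groups. Nothing in the plan shows how often that sequence would occur, or which group it would favour. A reader might also take the 6- and 12-month assessment intervals as the length of the delay. As shown above, they are not sampling intervals.

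**Conclusion.** The inconsistency is real and can be verified on the page. One threshold for acute leukemia includes 20% and the other does not, in an operative endpoint rule, and no text reconciles them. Its reach is narrow: it concerns only readings of exactly 20%, in an exploratory secondary endpoint. Within that reach the consequence is a PFS event dated late or not recorded, provided the parenthesis in section 6.6 is applied literally.

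The claim of inconsistency rests on no numerical assumption. Its frequency, the length of any delay and the direction of any bias cannot be determined from the documents. The primary analysis is not affected. The change is worth making because it is specific and nearly free, and because it settles how a plausible round-number result is to be coded.

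**What to change.** 1. In section 6.6, replace the strict inequality with 20% or more, so that the PFS threshold matches exclusion criterion 1.
2. State that the event is dated at the first marrow or blood sample that meets the threshold.
3. State that the same rule applies to outcomes from Leukemia CRIS and from the CIBMTR SCTOD. Editing section 6.6 alone may not achieve this, because the documents do not say how the SCTOD defines leukemic progression or whether the study can alter that definition.

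**Cost.** The text change is one symbol and two short sentences. If data have already been collected, any readings of exactly 20% need to be re-checked and recoded. The study team also has to confirm that the SCTOD data allow the same rule. Sample size, power and the OS analysis need no change.
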